11.2 Management of Toxicities Related to Radiotherapy

Supportive Care During Radiotherapy

- Antiemetics can be ordered at the discretion of the treating radiation oncologist.
- Mucositis/esophagitis may be ameliorated with sucralfate or gastrointestinal cocktail (e.g. Tyleon #3 suspension, benadryl elixir, Maalox, viscous lidocaine).
- Intravenous hydration is recommended in patients with inadequate oral intake.
- Treatment-related diarrhea can be managed with loperamide.

12.0 CRITERIA FOR THERAPEUTIC RESPONSE/OUTCOME ASSESSMENT

12.1 Primary Endpoint:

To compare overall response rate (ORR) in non irradiated lesions during the first 96 weeks after treatment initiation as determined by the investigator using Response Evaluation Criteria in Solid Tumors (RECIST) 1.1 criteria between patients receiving Nivolumab and SBRT to those receiving Nivolumab alone. ORR rate is defined as the number of patients randomized to a given arm with a best overall response (BOR) of complete response (CR) or partial response (PR) divided by the total number of patients randomized to the given arm.

To serially evaluate tumor response to therapy, it is necessary to estimate the overall tumor burden at baseline and use this as a comparator for subsequent measurements. Measurable disease is defined by the presence of at least one measurable tumor lesion. At baseline, tumor lesions/lymph nodes will be categorized as measurable or nonmeasurable.

12.1.1 Measurable Lesions

Of note, for purposes of this study, irradiated lesions are not considered measurable.

Measurable lesions must be accurately measured in at least one dimension (longest diameter in the plane of the measurement to be recorded) with a minimum size of:

- 10mm by CT/MRI scan
- Malignant lymph nodes: to be considered pathologically enlarged and measurable, a lymph node must be ≥ 15 mm in short axis when assessed by CT scan. At baseline and in follow-up, only the short axis will be measured and followed.

12.1.2 Non-measurable lesions

- All other lesions including small lesions (longest diameter <10 mm or pathological lymph nodes with ≥ 10 to <15 mm short axis), as well as truly non-measurable lesions.
- Lesions considered to be truly nonmeasurable include: leptomeningeal disease, ascites, pleural or pericardial effusion, inflammatory breast disease, lymphangitic involvement of skin or lung.

12.1.3 Special Considerations Regarding Lesion Measurability

- Bone scan, PET scan or plain films are inadequate to measure bone lesions. However, these techniques can be used to confirm the presence of disappearance of bone lesions.
- Lytic bone lesions or mixed lytic-blastic lesions with identifiable soft tissue components that can be evaluated by cross sectional imaging techniques such as CT/MRI can be considered as measurable lesions if the SOFT TISSUE component meets the definition of measurability.
- Blastic bone lesions are non-measurable.

12.1.4 Cystic Lesions

- Lesions that meet the criteria for radiographically defined simple cysts should not be considered as malignant lesions since they are, by definition simple cysts.
- "Cystic lesions" thought to represent cystic metastases can be considered as measurable lesions, if they meet the aforementioned definition of measurability. However, non-cystic lesions are preferred.

12.1.5 Lesions with Prior Local Treatment

- Tumor lesions situated in the previously irradiated area can be included as target lesions as long as there is documented radiographic disease progression in that site after completion of radiotherapy.

12.1.6 Baseline Documentation of "Target" and "Non-Target" Lesions

12.1.6.1 Target Lesions

When more than one measurable lesion is present at baseline all lesions up to a maximum of five lesions total representative of all involved organs should be identified as target lesions and will be recorded and measured at baseline.

Target lesions should be selected on the basis of their size, be representative of all involved organs, and should lend themselves to reproducible repeated measurements.

A sum of diameters (longest for non-nodal lesions, short axis for nodal lesions) for all target lesions will be calculated and reported as the baseline sum diameters. If lymph nodes are to be included in the sum, then as noted below, only the short axis is added into the sum. The baseline sum diameters will be used as reference to further characterize any objective tumor regression in the measurable dimension of the disease.

12.1.6.2 Non-Target Lesions

All other lesions (or sites of disease) including pathological lymph nodes should be identified as non-target lesions and should be recorded at baseline. Measurements are NOT required and these lesions should be followed as “present”, “absent”, or in rare cases, “unequivocal progression”. In addition, it is possible to record multiple non-target lesions involving the same organ as a single item on the case record form.

12.1.7 Tumor Response Evaluation

Complete Response (CR): disappearance of all target lesions. Any pathological lymph nodes must have reduction in short axis to <10mm.

Partial Response (PR): at least a 30% decrease in the sum of diameters of target lesions, taking as a reference the baseline sum of diameters.

Progressive Disease (PD): at least a 20% increase in the sum of diameters of target lesions, taking as a reference the smallest sum on study (this includes the baseline sum if that is the smallest on study). IN addition the relative increase of 20%, the sum must also demonstrate an absolute increase of at least 5mm. Note: the appearance of one or more new lesions is also considered progression.

Stable Disease (SD): neither sufficient shrinkage to qualify for PR nor sufficient increase to qualify for PD, taking as a reference the smallest sum diameters while on study.

12.1.8 Evaluation of Non-Target Lesions

While some non-target lesions may actually be measurable, they need not be measured and instead should be assessed only qualitatively at the time points specified.

Complete Response (CR): disappearance of all non-target lesions. All lymph nodes must be non-pathological in size (<10mm short axis).

Non-CR/Non-PD: persistence of one or more non-target lesions.

Progressive Disease: unequivocal progression of existing non-target lesions (Note: the appearance of one or more new lesions is also considered progression) or the appearance of new malignant lesions. The finding of new lesions should be unequivocal.

- To achieve unequivocal progression on the basis of non-target disease, there must be an overall level of substantial worsening in non-target disease such that, even in the presence of SD or PR in target disease, the overall tumor burden has increased sufficiently to merit discontinuation of therapy.
- A modest “increase” in the size of one or more non-target lesions is usually not sufficient to qualify for unequivocal progression status.
- If unequivocal progression is seen, the subject should be considered to have had an overall PD at that point.

FDG-PET Evaluation

While FDG-PET response assessments need additional study, it is sometimes reasonable to incorporate the use of qualitative assessment of FDG-PET scanning to complement CT scanning in assessment of progression, particularly new disease. New lesions on the basis of FDG-PET imaging can be identified according to the following algorithm.

- Negative FDG-PET at baseline with a positive FDG-PET at follow-up is a sign of PD based on a new lesion.
- No FDG-PET at baseline and a positive FDG-PET at follow-up:
 - If positive PET at follow-up corresponds to new site of disease, this is PD
 - IF the positive PET at follow-up is not confirmed as a new site of disease on CT, additional follow-up CT scans are needed to determine if there is truly progression occurring at that site.
 - If the positive PET at follow-up corresponds to a pre-existing site of disease on CT that is not progressing on the basis of the anatomic images, this is not PD.

12.1.9 Response Criteria

Table 1 – Time point response: patients with target (+/- non-target) disease.

Target lesions	Non-target lesions	New lesions	Overall response
CR	CR	No	CR
CR	Non-CR/non-PD	No	PR
CR	Not evaluated	No	PR
PR	Non-PD or not all evaluated	No	PR
SD	Non-PD or not all evaluated	No	SD
Not all evaluated	Non-PD	No	NE
PD	Any	Yes or No	PD
Any	PD	Yes or No	PD
Any	Any	Yes	PD

CR = complete response, PR = partial response, SD = stable disease, PD = progressive disease, and NE = inevaluable.

Table 2 – Time point response: patients with non-target disease only.

Non-target lesions	New lesions	Overall response
CR	No	CR
Non-CR/non-PD	No	Non-CR/non-PD ^a
Not all evaluated	No	NE
Unequivocal PD	Yes or No	PD
Any	Yes	PD

CR = complete response, PD = progressive disease, and NE = inevaluable.
 a 'Non-CR/non-PD' is preferred over 'stable disease' for non-target disease since SD is increasingly used as endpoint for assessment of efficacy in some trials so to assign this category when no lesions can be measured is not advised.

The best overall response is determined once all the data for the subjects is known. It is the best response recorded from the start of the study treatment until, in our own trial, 2 years. The subjects best overall response will depend on the findings of both target and non-target disease and will also take into consideration the appearance of new lesions.

Best response is defined as the best response at all time points. When SD is believed to be the best response, it must also meet protocol specified minimum time from baseline (8 weeks). If the minimum time is not met when SD is otherwise the best time point response, the subjects best response depends on the subsequent assessments. For

example, a subject who has SD at first assessment, PD at second and does not meet minimum duration of SD, will have best response of PD. The same subject lost to follow-up after the first SD assessment will be considered not evaluable.

12.1.10 Verification Scans

- Verification of Response: confirmation of response (CR or PR) is required. Confirmed CR or PR will be claimed only if the criteria for each are met at a subsequent time point (minimum 4 weeks after criteria for an objective response are first met).
- Verification of Progression: progression of disease should be verified in cases where progression is equivocal. If repeat scans confirm PD, then progression should be declared using the date of the initial scan. If repeat scans do not confirm PD, then the subject is considered not to have progressive disease per RECIST 1.1.

Table 3 – Best overall response when confirmation of CR and PR required.

Overall response First time point	Overall response Subsequent time point	BEST overall response
CR	CR	CR
CR	PR	SD, PD or PR ^a
CR	SD	SD provided minimum criteria for SD duration met, otherwise, PD
CR	PD	SD provided minimum criteria for SD duration met, otherwise, PD
CR	NE	SD provided minimum criteria for SD duration met, otherwise NE
PR	CR	PR
PR	PR	PR
PR	SD	SD
PR	PD	SD provided minimum criteria for SD duration met, otherwise, PD
PR	NE	SD provided minimum criteria for SD duration met, otherwise NE
NE	NE	NE

CR = complete response, PR = partial response, SD = stable disease, PD = progressive disease, and NE = inevaluable.

^a If a CR is truly met at first time point, then any disease seen at a subsequent time point, even disease meeting PR criteria relative to baseline, makes the disease PD at that point (since disease must have reappeared after CR). Best response would depend on whether minimum duration for SD was met. However, sometimes 'CR' may be claimed when subsequent scans suggest small lesions were likely still present and in fact the patient had PR, not CR at the first time point. Under these circumstances, the original CR should be changed to PR and the best response is PR.

12.2 Secondary End Points:

12.2.1 Duration of Response

The duration of objective response is measured from the time measurement criteria are first met for confirmed PR/CR until the first date the progressive disease is objectively documented (taking as a reference for progressive disease the smallest measurements recorded on study). Duration of response will be measured from the time, in months, that the criteria for objective response are first met until the date of a progression event. A subject with objective response who does not have a progression event at 96 weeks will be censored.

12.2.2 Overall Survival

Overall survival is defined as the time from randomization to the date of death from any cause. For subjects that are alive, their survival time will be censored at the date of last contact. Overall survival will be censored for subjects at the date of randomization if they were randomized but had no follow-up.

12.2.3 Progression Free Survival (PFS)

PFS is defined as the time from randomization to the date of RECIST-defined progressive disease (PD) or death from any cause. For subjects that are alive with CR, PR, or SD, they will be censored at the end of the two year, study mandated tumor assessments. PFS will be censored for subject at the date of randomization if they were randomized but had no follow-up.

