- Nivolumab is administered as an IV infusion every 14 days (+/- 2 days) until disease progression (or until discontinuation of Nivolumab in subjects receiving beyond progression), unacceptable toxicity, or withdrawal of consent.
- Response is evaluated using RECIST 1.1 criteria.

The first tumor assessment of non-irradiated lesions will occur at week 8 (+/- 2 weeks) after treatment initiation and then every 8 weeks (+/-2 weeks) for the first 48 weeks and then every 12 weeks (+/-2 weeks) until documented progression or week 96 whichever occurs first. CT or MRI images of chest, abdomen, pelvis, head, neck, and all known sites of disease should be obtained. The same imaging modality that was used as baseline should be used at all subsequent evaluations.

- After week 96 of treatment, patients will be contacted every 3 months for survival. This can be done by phone if the patient is unable to come into clinic for routine follow-up.
- Treatment phase will conclude at the time of study drug discontinuation.
- Imaging can continue per institutional preference past 96 weeks, however, RECIST reads are not required.

Follow-Up Phase

- Begins at the conclusion of Nivolumab therapy.

- Subjects will have one follow-up visit for safety within approximately 100 days from the last dose of Nivolumab.
- Subjects who discontinue treatment for reasons other than tumor progression will continue to have tumor assessments per prior schedule (e.g. every 8 weeks for the first 48 weeks and then every 12 weeks until week 96).
- Follow-up (phone or visit) will continue to occur every 3 months for survival information.

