14.0 BIOSTATISTICS

11.1 Primary Objective

The primary objective of this study is to compare best overall response (BOR) rate by 96 weeks as determined by the investigator using RECIST 1.1 criteria between patients receiving Nivolumab and SBRT and those receiving Nivolumab alone. BOR rate is defined as the number of patients randomized to a given arm with a best overall response of complete response (CR) or partial response (PR) of non-irradiated lesions divided by the total number of patients randomized to the given arm. In order to ascertain this endpoint, efforts will be made so that patients will be followed for 96 weeks or until progression of disease (and treatment cessation), whichever comes first.

Based upon an estimated ORR of 15% in a PD-L1 unselected population in the Nivolumab alone arm (based on data from Siewert, et al; see background) and an ORR of 45% in the Nivolumab and SBRT arm, the enrollment of 54 patients with a two-sample proportion test will provide a one-sided alpha of 0.10 and a power of 0.80. Assuming a 10% drop-out rate, we will enroll a total of 60 patients. Patients will be randomized to the two treatment arms in a 1:1 ratio. Patients will be stratified based upon viral status (virus negative versus virus positive; virus status is defined by EBV (EBER testing) or HPV (p16, HPV ISH, HPV PCR) testing). Assuming a constant enrollment of 3 subjects per month, it would take approximately 20 months to randomize 60 patients. Calculations were completed using software R 3.1.1 and EAST 6.

To ensure eligible endpoints are well defined, a minimum of 6 months of follow up after treatment initiation is required. Patients lost to follow-up prior to 6 months (24 week scan) will be replaced, regardless of response. Patients lost to follow-up between 6 months and 24 months will be included in the ORR calculation.

Secondary objectives:

OS and PFS will be evaluated by the regular survival analysis tools such as Kaplan-Meier and competing risks methods. Comparisons will be conducted between the two arms by the stratified log-rank test and Gray's test.

The DOR will be calculated from the time of response to progression or last follow up and analyzed using the Kaplan-Meier method among patients who showed response.

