For the exploratory objectives, all lab measurements will be summarized and descriptive statistics will be provided. When correlation between lab measurements and treatment outcomes are of interest, Wilcoxon rank sum tests will be conducted to examine the difference between responders and non-responders within each arm. An exploratory multivariate logistic regression analysis to determine whether, once adjusted for relevant clinical covariates and treatment arm, tumor PD-L1 or serum immunophenotypic changes predict for response to Nivolumab.

To clarify we define population for the above analyses

- Randomized subjects for ORR analysis: all enrolled subjects who were randomized and provided at least 6 months of follow-up after treatment initiation. This is the dataset for the primary objective and irORR.
- All randomized subjects: all enrolled subjects who were randomized. This is the dataset for baseline demographics and time-to-event endpoints (PFS, OS).
- Treated subjects: all randomized subjects who received at least one dose of study drug. This is the dataset for safety evaluation. For instance, if a subject receives a single dose of Nivolumab but withdraws from study prior to the first dose of radiation, that subject will be considered treated.
- Biomarker Subjects: all randomized subjects with available biomarker data.
- PRO subjects: all subjects with available Patient Reported Outcomes (PRO) data.

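### The PFS censoring rule credits patients who stop scans but are known to be alive with progression-free time up to about week 96, and gives no rule for some other losses

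*Combined protocol and SAP*

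**What the plan says.** Section 12.2.3 runs PFS from randomization to RECIST progression or death from any cause. It has two censoring rules. Subjects with no follow-up are censored at randomization. For the rest: "alive with CR, PR, or SD, they will be censored at the end of the two year, study mandated tumor assessments". No other section gives a PFS censoring date.

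Overall survival, in Section 12.2.2, uses a patient-specific date: "their survival time will be censored at the date of last contact".

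Three other places bear on who meets the PFS rule:

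- Section 4.2 (Intervention) ends mandated scans at progression or week 96. Patients who stop treatment without progression keep the scan schedule. Survival contact goes on separately: "Follow-up (phone or visit) will continue to occur every 3 months for survival information".
- Section 14.0 foresees loss to follow-up, but deals with it only for ORR: "Patients lost to follow-up prior to 6 months (24 week scan) will be replaced, regardless of response". Losses between 6 and 24 months stay in the ORR calculation.
- The analysis populations at the end of Section 14.0 put all randomized subjects into PFS and OS, so the ORR replacement rule does not remove early losses from PFS.

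**The concern.** Progression is seen on scans, so a patient is known to be progression-free only up to the last evaluable scan. The written rule replaces that date with the end of the two-year schedule. Between the two dates the patient stays in the risk set and cannot have a progression event, because nobody is looking for one. Only death can end the interval.

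Two things are at stake. The Kaplan-Meier PFS curve can be distorted, usually upward. If the arms lose patients to scans at different rates, the distortion also differs by arm and the log-rank comparison no longer has its nominal error rate. The trial is open label, so unequal loss is possible.

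There is also a gap. A patient with some follow-up but unknown vital status is not known to be alive, and a patient without an evaluable post-baseline scan has no on-study response status. Neither PFS rule fits either of them, so their dates would have to be chosen after the data are in.

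**Working it through.** **Plan's own figures.** The plan states no power, event count, alpha or sidedness for PFS, so there is no PFS figure to reproduce. The 10% drop-out in Section 14.0 is an allowance for the ORR sample size (54 / 0.90 = 60). It is borrowed below only as a scale.

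**Step 1. Credited time, from the scan schedule alone.** Extra weeks = 96 − week of last scan; months = weeks × 7 / 30.4375.

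| Last scan (week) | Extra weeks | Months |
|---|---|---|
| 8 | 88 | 20.2 |
| 24 | 72 | 16.6 |
| 48 | 48 | 11.0 |

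Week 96 is approximate on the PFS clock. Scans are timed from treatment start, which may follow randomization by up to 14 + 4 = 18 days, so week 96 can fall at 96 + 18/7 = 98.6 weeks.

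**Step 2. Effect on 12-month PFS (illustration).** Assumptions:

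- PFS is exponential with median M = 3, 4 or 6 months. Section 3.2 cites a median of at most 6 months for recurrent disease with a metastatic component.
- 10% of patients are assigned a drop-out time d, uniform over months 0 to 6 and unrelated to prognosis.
- After drop-out all deaths are known and occur at a median of m = 4, 8 or 16 months.

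With h = ln2/M and k = ln2/m, the written rule gives

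PFS(12) = 0.9·exp(−12h) + 0.1·E[exp(−hd − k(12−d))],

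where E[·] = exp(−12k)·(1 − exp(−6(h−k))) / (6(h−k)), and equals exp(−12k) when h = k.

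For M = 4 and m = 8: exp(−12h) = 0.125; E = 0.3536 × 0.7798 = 0.2757; PFS(12) = 0.1125 + 0.0276 = 0.1401.

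| M (months) | True | m = 4 | m = 8 | m = 16 |
|---|---|---|---|---|
| 3 | 6.3% | 6.7% | 8.0% | 9.2% |
| 4 | 12.5% | 12.5% | 14.0% | 15.4% |
| 6 | 25.0% | 24.0% | 25.7% | 27.3% |

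The bias is zero when death after drop-out is as fast as progression or death would have been (M = m = 4), and negative when it is faster (M = 6, m = 4). With M = 4, the number lost before an event is 60 × 0.1 × E[exp(−hd)] = 6 × 0.622 = 3.7 of 60. The model counts all of them as meeting the rule, including those lost before the week-8 scan, so it leans towards too large an effect.

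**Step 3. Log-rank test under no true difference.** Simulation of 100,000 trials, 30 per arm, M = 4, deaths captured at m = 8, administrative end at 22.1 months. The test was unstratified, whereas the plan's is stratified. Monte Carlo error is at most 0.0014. Cells show the written rule / censoring at drop-out.

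| Drop-out, control / SBRT | One-sided 0.05 | Two-sided 0.05 |
|---|---|---|
| 10% / 10% | 0.054 / 0.054 | 0.056 / 0.057 |
| 0% / 10% | 0.074 / 0.053 | 0.060 / 0.056 |
| 10% / 0% | 0.039 / 0.056 | 0.061 / 0.057 |

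With deaths at m = 4, the one-sided 0.05 error is 0.053 in both unequal cases.

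**The case against.** The best defence is that the two-year date is only the administrative end of follow-up. Section 14.0 says that PFS will be analysed with ordinary Kaplan-Meier methods, under which an incompletely followed patient is censored when observation stops. A competent analyst might well do that. But the section names a fixed date for everyone alive with CR, PR or SD, gives no last-scan date, and does use a patient-specific date for OS. The defence describes good practice that the text does not state.

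The other limits stand. Scans continue after treatment stops without progression, and known deaths remain PFS events, so only patients who truly stop scans are affected. Section 13.3 dates progression at the first event, and the palliative radiotherapy rule in Section 6.2 counts such patients as progressed, which narrows the group further. The documents give no drop-out by arm; the 10% against 0% contrast is an assumption.

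A reader might infer three stronger things, none of which the documents support:

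- That every lost patient is carried to week 96, including those whose deaths are never learned of. The rule requires the subject to be alive, so it does not reach patients of unknown status.
- That the PFS comparison is seriously anti-conservative. This needs unequal loss, and the direction depends on which arm loses more.
- That duration of response is contradictory. Section 12.2.1 says "A subject with objective response who does not have a progression event at 96 weeks will be censored", and Section 14.0 has it "calculated from the time of response to progression or last follow up". These can be read together as last follow-up capped at week 96. Not counting death as an event is a less usual but coherent definition, and no effect has been shown.

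**Conclusion.** The point holds for PFS. As written, Section 12.2.3 counts unscanned time as progression-free for patients who stop scans and are known to be alive, and leaves other partly followed patients without a rule. The credited time per patient (48 to 88 weeks in the examples) follows from the schedule alone. The effect on the results is likely to be small: across the assumed medians, 12-month PFS moves by between −1.0 and +2.9 percentage points. The test is nominal with equal loss. Its one-sided 0.05 error is about 0.07 if only the SBRT arm loses 10%, and about 0.04 if only the control arm does; the two-sided error is essentially unchanged. These figures rest on exponential PFS, 10% drop-out, captured deaths and drop-out unrelated to prognosis. PFS is a secondary endpoint; ORR and the sample size are not touched. It should be settled before the analysis.

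**What to change.** In Section 12.2.3, keep death from any cause as an event. Censor patients without progression or death at their last evaluable tumour assessment, no later than week 96, or at randomization if there is none. Report the number and timing of loss to scans by arm.

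Optionally, use one wording for the end and censoring of duration of response in Sections 12.2.1 and 14.0, and state how death without documented progression is handled.

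The cost is wording only, since the plan already collects scan and death dates. PFS may look slightly less favourable. Censoring at the last scan still assumes that loss to scans is unrelated to prognosis, which is why the report of losses by arm is needed.
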